4. SIGNIFICANCE: State concisely the importance of this project by relating the purpose to broader, long-range objectives. Providing optimal post-operative analgesia to our patients is important to improve

patient satisfaction, decrease opioid related side effects, and promote early recovery and discharge from the hospital. This study will help determine if using liposomal bupivacaine alone or in combination with bupivacaine hydrochloride provides enhanced post-operative analgesia.

5. SUBJECTS IN THE PROJECT:

- a. State the inclusion and exclusion criteria for enrollment of subjects. Inclusion criteria: elective open abdominal hysterectomy with a midline incision, age>18, ASA 1-3. Exclusion criteria: patient with a chronic pain condition, major unexpected surgical complication, unexpected prolonged intubation, patient refusal, local anesthetic allergy, any contraindication to regional anesthesia, and greater than two attempts for TAP block by residents and greater than one attempt by staff anesthesiologist.
- b. Describe the control population (if utilized) and justify its selection. Our current standard practice is to use 0.25% bupivacaine for TAP blocks, therefore, the control population is the group receiving 0.25% Bupivacaine.
- c. Support the likelihood of recruiting the number of subjects required to complete the project. Relate this to other projects recruiting similar subjects. We estimate that 100-150 patients undergo open abdominal hysterectomy with a midline incision at Henry Ford Hospital each year. We anticipate an 80% or higher recruitment rate. Therefore, we anticipate recruiting 90 patients within a year. No other studies are recruiting similar patients.

6. PROJECT DESIGN AND PROTOCOL:

- a. Describe the experimental design/methodology. Prospective randomized observer-blinded controlled study.

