- b. Outline the protocol, corresponding it to the specific aims; identify the data or endpoints to be analyzed to reach the specific aims. All eligible patients will be seen in the pre-operative holding area to discuss the study. Informed consent will be obtained at that time. The patient will be randomized to one of three groups by random envelope selection. Group 1 will receive a TAP block with a total of 60 mL 0.25% bupivacaine hydrochloride. Group 2 will receive a TAP block with a total of 20 mL of liposomal bupivacaine and 40 mL normal saline. Group 3 will receive a TAP block with a total of 20 mL of liposomal bupivacaine and 40 mL 0.25% bupivacaine hydrochloride. Our standard sedation protocol for all patients receiving any nerve block is to provide a maximum of 2 mg midazolam and 100 mcg fentanyl during procedure. The patient will be monitored per our routine practice standards. The patients will undergo the surgical procedure with general anesthesia as directed by the attending anesthesiologist. All patients will receive 30 mg ketorolac IV. If ketorolac is contraindication, the patient will receive 1000 mg acetaminophen IV. The patient will be recovered and receive routine post-operative care. Patients will be assessed immediately post-operatively in the post-anesthesia care unit (PACU), and one time during each of the following time periods: 0-24 hrs post-operatively, 25-48 hours post-operatively, and 49-72 hours post-operatively. Primary outcomes are total opioid consumption, time to the first opioid administration, and pain score during the above mentioned time periods. Secondary outcomes are patient satisfaction, length of stay in hospital, timing of ambulation, presence of nausea and vomiting, evidence of local anesthetic toxicity and any postoperative hemodynamic instability.
- c. Discuss potential limitations and difficulties in the protocol. We don't anticipate any difficulties with this protocol since patients typically receive a TAP block for post-operative analgesia for open abdominal hysterectomy at Henry Ford Hospital. One limitation of our protocol is that it is not double-blinded. Liposomal bupivacaine is white and distinctive from bupivacaine hydrochloride. Therefore, the anesthesiologist performing the block cannot be blinded to group selection. All other care team members including anesthesia team, surgical team, and floor nurses, will be blinded to the group selection.

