repeated outcomes. Ideally these time points are at baseline, 6 hours, 12 hours, 18 hours, 24 hours, 36 hours, 48 hours, 60 hours and 72 hours. Continuous variables will be summarized with n, mean, standard deviation and range. Frequency counts and percentage will be provided for categorical data. Estimates for averages and proportions will also include 95 % confidence intervals. One-way Analysis of Variance(ANOVA) will be used to assess the efficacy of three anesthetic bupivacaine formulas (G1: bupivacaine HCL; G2: liposomal bupivacaine ; G3: liposomal bupivacaine + bupivacaine HCL) on total opioid consumption, patient satisfaction, length of stay in hospital as well as timing of ambulation. Generalized Estimating Equations (GEE) will be utilized to evaluate the effects of these three anesthetic formulas on repeated measures of pain scores, presence of nausea and vomiting, evidence of local anesthetic toxicity and any postoperative hemodynamic instability. Cox proportion hazard models will be applied to assess the effect of these anesthetic formulas on the time to first opioid administration. The statistical analysis will be obtained by using SAS 9.4 and the tests are claimed to be significant if the p- values are less than 0.05.

8. JUSTIFICATION FOR NUMBER OF SUBJECTS OR DATA:

- a. State the number of subjects or data points to be analyzed in the project at this institution and the total number for multicenter studies. The Committee recommends consultation with the Division of Biostatistics and Research Epidemiology [contact]. Total 90 subjects are expected given at least 80% recruitment rate of total 100-150 patients undergo open abdominal hysterectomy at Henry Ford Hospital each year.
- b. Describe the statistical justification for this number of subjects or data points. Total 90 patients (30 for each of these 3 groups) will have 80% power to detect the effect size of 0.33 by using One- Way ANOVA for assessing the effects of three formulas on total opioid consumption; and an effect size of 0.24 can be detected with 80% power assuming 0.5 correlation among repeated measures by using repeated One - Way ANOVA for assessing the effects of three formulas on pain scores.

FORM A

HENRY FORD HEALTH SYSTEM (IRB) DRUG/SUBSTANCE INFORMATION

(This form must be completed for each individual drug or substance -investigational or marketed- that is being administered as part of this research study)

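### Section 7's single p<0.05 claim rule also covers the six secondary outcomes, with no order, adjustment or supportive label, so at least one false secondary claim has a chance of about 14% to 26% if the formulations do not differ

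*Combined protocol and SAP*

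**What the plan says.** Section 6b separates two tiers of outcome. For the first: "Primary outcomes are total opioid consumption, time to the first opioid administration, and pain score during the above mentioned time periods". For the second: "Secondary outcomes are patient satisfaction, length of stay in hospital, timing of ambulation, presence of nausea and vomiting, evidence of local anesthetic toxicity", to which it adds "any postoperative hemodynamic instability". That makes three primary and six secondary outcomes.

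Section 7 does not carry the two tiers forward. It assigns methods by type of data:

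- One-way ANOVA is applied "on total opioid consumption, patient satisfaction, length of stay in hospital as well as timing of ambulation": one primary outcome and three secondary ones in the same sentence.
- GEE is applied to "repeated measures of pain scores, presence of nausea and vomiting, evidence of local anesthetic toxicity and any postoperative hemodynamic instability": one primary outcome and the other three secondary ones.
- A Cox model is applied to the remaining primary outcome, time to first opioid.

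The section then ends with the claim rule: "the tests are claimed to be significant if the p- values are less than 0.05". The rule is not restricted to any tier. Section 7 also promises 95% confidence intervals for averages and proportions, but does not mention intervals for differences between groups.

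**The concern.** The difficulty is a written rule for making claims, which is more than silence about multiplicity. Read literally, section 7 lets any secondary outcome with p below 0.05 be called significant, even if every primary result is null. Across six such tests, the chance of at least one false call is well above the chance for one.

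What is at stake is the trial's conclusion. With 30 patients per arm, null primaries together with one nominally significant secondary could well occur, and the plan gives no guidance on how to describe it. Section 4 presents the value of good analgesia partly through "patient satisfaction, decrease opioid related side effects, and promote early recovery and discharge from the hospital", which overlaps with the secondary list. A secondary finding could therefore be given more weight than it can bear. That is a risk, not a certainty.

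**Working it through.** **Inputs from the documents.** Three groups of 30 (section 8b); six secondary outcomes (section 6b), three tested by ANOVA and three by GEE (section 7); threshold 0.05 for each test (section 7).

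**Assumptions.** No difference between formulations on any outcome; one overall three-group test per outcome; a common correlation between outcomes of 0 to 0.8. The 0.5 in section 8b is a correlation among repeated pain scores and does not apply here. All outcomes are simulated as normal and tested by a one-way F test, which only approximates the GEE analyses.

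**Step 1: the plan's own figure.** Section 8b says: "Total 90 patients (30 for each of these 3 groups) will have 80% power to detect the effect size of 0.33". The noncentrality is f² × N = 0.33² × 90 = 9.80. With 2 and 87 degrees of freedom and a 0.05 threshold, power is 79.3%, which agrees with the stated 80%. So 0.05 is the level for a single test; the documents state no error rate for a family of tests.

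**Step 2: independent outcomes.** The chance of at least one false rejection in K tests is 1 − 0.95^K.

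- K = 6: 1 − 0.95^6 = 1 − 0.735 = 26.5%.
- K = 4: 1 − 0.95^4 = 1 − 0.815 = 18.5%.

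The four are satisfaction, length of stay, ambulation, and nausea and vomiting. Toxicity and hemodynamic instability are left out of this second count because events may be too sparse for their tests to reject at the nominal rate.

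**Step 3: correlated outcomes.** Simulation of 3 × 30 patients, with F tests at 0.05. The last column adds the three primaries with the same common correlation and keeps only trials in which none of them is significant.

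| Assumed correlation | All six | Four benefit outcomes | Four, given three non-significant primaries |
|---|---|---|---|
| 0 | 26.5% | 18.5% | 18.5% |
| 0.3 | about 24% | about 17% | about 15–16% |
| 0.5 | about 21% | about 15–16% | about 12–13% |
| 0.8 | about 14% | about 11–12% | about 6% |

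The first row is the closed form; with independence, conditioning on the primaries changes nothing. Where a range is shown, repeated simulations differed by about a point. The last column falls faster because, when outcomes are correlated, null primaries make false secondaries less likely.

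**Step 4: would an adjustment work?** Requiring the smallest of K p-values to fall below 0.05/K, which is Holm's first step, brought the simulated chance to between 2.9% and 5.0%. For four outcomes the first threshold is 0.05/4 = 0.0125.

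**The case against.** The strongest reply is that the word secondary already means supportive, and that unadjusted secondary tests are common in small single-centre trials. The documents lend this some weight. Section 6b keeps the tiers apart, the specific aims and the hypothesis concern analgesia only, and both power statements in section 8b are for primary outcomes. A reader might infer from the shared threshold that the investigators regard the secondaries as confirmatory, or from section 4 that they plan claims on them. The text supports neither reading: the plan never uses such a label, and section 4 is general motivation. What stands against the reply is that section 7, the only place with a rule for claims, drops the distinction and applies the rule to every test.

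A second reply is that the plan contradicts no figure of its own. That is correct. It gives a per-test threshold and asserts no error rate across the secondary tests.

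A third is that confidence intervals are already planned. This is partly right: the stated intervals are for averages and proportions, and between-group differences are not mentioned.

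A fourth is that the three primary outcomes under the same rule are the weightier matter (1 − 0.95^3 = 14.3% if independent). That also stands, but correcting the primary rule alone would leave the secondary claims open.

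**Conclusion.** The point holds as a cheap improvement to what the plan allows to be concluded. If the formulations do not differ, the chance of at least one false significant secondary is about 14% to 26% for all six outcomes, about 12% to 18.5% for the four benefit outcomes, and about 6% to 18.5% for those four when all three primaries are non-significant. Each range runs from an assumed correlation of 0.8 down to 0 and depends on one overall test per outcome. Pairwise or time-point tests, which the plan does not specify, would raise the figures; sparse events would lower them.

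Two stronger readings should be avoided:

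- A reader might infer that null primaries would still be followed by a false benefit claim one time in five. For the four benefit outcomes no case in the table reaches 20%, and at correlation 0.8 the figure is close to the conventional 5%.
- A reader might infer that such a result would be reported as a proven benefit of one formulation. The planned tests are overall three-group comparisons with no specified pairwise contrasts, so a rejection would not by itself identify a formulation.

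**What to change.** In section 7, restrict the significance rule to the primary analysis and add a statement such as: *Secondary outcomes are supportive. They will be reported as between-group differences with 95% confidence intervals, in addition to the per-group intervals; p-values are nominal and no claim of significance will be made.* Toxicity and hemodynamic instability should be reported descriptively.

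If the investigators want formal claims on satisfaction, length of stay, ambulation or nausea and vomiting, one option is Holm across those four at a total of 0.05, tested only after a positive primary result. This is a choice, not a requirement.

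The cost is one or two sentences, with no added patients or data. The downside is that a lone secondary p-value just under 0.05 can no longer be called significant; under the Holm option the smallest of the four would have to be at or below 0.0125. The change is best made together with the rule for the three primary outcomes, since the same sentence governs both.

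### The 80% power stated in section 8b holds only if all 90 recruited patients are analysed, and the plan makes no allowance for the exclusions after randomisation that it lists itself

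*Combined protocol and SAP*

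**What the plan says.** Section 8b gives the power of an analysis of variance for total opioid consumption, one of the primary outcomes in section 6b: "Total 90 patients (30 for each of these 3 groups) will have 80% power to detect the effect size of 0.33 by using One- Way". Section 7 sets the significance level: "the tests are claimed to be significant if the p- values are less than 0.05".

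The 90 is also the recruitment figure. Section 5c says "We anticipate an 80% or higher recruitment rate. Therefore, we anticipate recruiting 90 patients within a year". The form's item 8a asks how many subjects will be analysed, and the answer is again a count of expected recruits: "Total 90 subjects are expected given at least 80% recruitment rate of total 100-150 patients undergo open abdominal hysterectomy" each year.

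Under section 6b, patients consent and are randomised in the pre-operative holding area, before the block and before surgery. The exclusion criteria in section 5a include "major unexpected surgical complication, unexpected prolonged intubation, patient refusal" and, at the end of the list, more than a set number of attempts at the block. The documents contain no allowance for loss, no definition of the analysis population and no statement on whether an excluded patient is replaced.

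**The concern.** One number does two jobs. Ninety is how many patients the investigators expect to recruit, and it is also how many must contribute an opioid total for the stated power to hold. The two agree only if nobody is lost. Yet section 5a foresees loss: a surgical complication, a prolonged intubation and too many block attempts can all be known only after the envelope has been drawn.

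Section 8b is the plan's only statement of what the trial can detect on opioid consumption. Section 3a describes similar analgesia with the two formulations in local experience, and an earlier randomised trial with no difference in the first 48 hours, so a null result is plausible. A reader of such a result would turn to 8b and take it that the trial had 80% power at 0.33. With fewer than 90 analysed, that would be too favourable.

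**Working it through.** **Inputs**
- Three equal groups, N = 90, effect size 0.33, stated power 80% (section 8b).
- Alpha 0.05 (section 7), applied to the overall F test.
- The plan does not name the effect-size metric. I read it as Cohen's f, an assumption supported by the fact that it reproduces the stated power.
- Loss rates of 5%, 10% and 20% are my assumptions, because the documents give none.

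**Formula.** Power = P[F′(2, N − 3, λ) > F₀.₉₅(2, N − 3)], where F′ is the noncentral F distribution and λ = N × f².

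**Step 1: reproduce the plan's figure.** f² = 0.33² = 0.1089. At N = 90, λ = 90 × 0.1089 = 9.80 with 2 and 87 degrees of freedom, and power is 79.3%. Solving for the f that gives exactly 80% at N = 90 yields 0.333, which rounds to the stated 0.33. The plan's figure is reproduced.

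**Step 2: look for slack.** At exactly f = 0.33, 80% power needs 92 patients, or 93 with equal groups. Ninety is therefore already at the limit, and any loss takes power further below 80%.

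**Step 3: allow for loss from 90 randomised.**

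| Assumed loss | Analysed | λ = N × 0.1089 | Power at f = 0.33 | f detectable with 80% power |
|---|---|---|---|---|
| 0% | 90 | 9.80 | 79.3% | 0.333 |
| about 5% | 85 | 9.26 | 76.7% | 0.343 |
| 10% | 81 | 8.82 | 74.5% | 0.352 |
| 20% | 72 | 7.84 | 68.8% | 0.374 |

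The formula treats the groups as equal in size, which is only approximate at 85. The drop in power from 79.3% is 2.6 points at about 5% loss, 4.8 points at 10% and 10.5 points at 20%.

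**Step 4: timing of the exclusions.** Section 6b puts randomisation before the block and surgery. Of the criteria in 5a, three can arise only afterwards: surgical complication, prolonged intubation and block attempts. Patient refusal, which stands beside them in the list, can be read as a criterion applied before entry, so I do not count it.

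**The case against.** **Section 8b contains no arithmetic error.** This stands. The figure is right for 90 analysed; what is missing is the assumption that links 90 analysed to 90 recruited.

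**The prompt in 8a asks for the number analysed, so 90 may be an evaluable target with more patients enrolled to reach it.** This stands in part. The plan is silent on replacement, and a reader who infers that it forbids replacement goes further than the documents. But 5c speaks of recruiting 90, and the answer in 8a derives 90 from the expected recruitment rate. Nothing in the plan provides for a larger enrolment. At an assumed 10% loss, keeping 90 analysed would take 90 / 0.9 = 100.

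**The loss may be small.** Randomisation is close to surgery, and opioid use is a cumulative total for which the documents give no sign of much missing data. This is fair, and at about 5% loss the effect is under three points. The larger drops rest on rates that the documents do not support. The planned 95% confidence intervals (section 7) also mean that a null result need not be read from the power alone. Neither point makes the statement in 8b correct once patients are excluded.

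**A stronger reading is that recruitment will fall short as well.** Eighty per cent of 100 is 80, which is below 90. The documents do not support this as a threat to power. The rate is given as 80% or higher, and 80% of 100 to 150 is 80 to 120, which brackets 90. The one-year period is an anticipation given under a request for a tentative schedule, and no passage makes it a stopping rule, so slow accrual could be met by recruiting for longer.

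**Conclusion.** The point holds as a gap in the sample-size justification. The stated 80% power applies to 90 analysed patients, and the plan's own exclusions make a smaller number foreseeable without allowing for it. At an assumed 10% loss, power at 0.33 is 74.5% rather than 79.3%, and the detectable effect is 0.352 rather than 0.333. The size is modest, but it runs in one direction only, because there is no margin at 90.

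This rests on three assumptions: the effect size is Cohen's f; patients who meet a 5a criterion after randomisation leave the analysis, which is inferred from their place in the exclusion list; and the loss rates are illustrative. The point concerns the stated power only. It does not address any bias from removing patients after randomisation.

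**What to change.** Keep 90 as the number randomised and restate 8b for the number expected to be analysed. For example: *Ninety patients will be randomised. Allowing for 10% not analysed (an assumption), 81 patients give 80% power for an effect size (Cohen's f) of 0.35; at 0.33 the power is about 74%.* The investigators should put in their own expected loss rate if they have one, and mark it as an assumption.

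The cost is a change of wording in 8b. No patients are added, and neither the analysis nor the conduct of the trial changes. The downside is that the stated detectable effect becomes slightly less favourable.

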A randomized-controlled trial comparing liposomal bupivacaine, plain bupivacaine, and the mixture of liposomal bupivacaine and plain bupivacaine in transversus abdominus plane block for postoperative analgesia for open abdominal hysterectomies

Clinical Trials registration number: NCT03250507

Document date: 6/22/2016

HENRY FORD HEALTH SYSTEM IRB PROTOCOL FORMAT

Appendix 1

(Incomplete applications will be returned, & inadequate responses may lead to a delay in review.) You may mark your responses in the shaded areas following each question. Supporting documents (articles, drug toxicity information, etc.) must be submitted when applicable. A "See Attached" response will not be accepted for review. Be concise & clear.

Directions:

Sponsored protocol: If you have a sponsored protocol (e.g., pharmaceutical), a grant application (e.g., National Institutes of Health), or another peer-reviewed protocol, you may submit that protocol/application along with the application elements. It is the responsibility of the Principal Investigator to assure, however, that the protocol/application contains the information requested in this "IRB Protocol Format". Additional sheets should be attached to the protocol/application as necessary to provide the information (e.g., a description of the process of consent) required for IRB review. When available, the Investigator's Brochure must be submitted along with the research protocol, or a summary of the preclinical/animal data and any relevant clinical data.

Physician Initiated protocol: If you have not been provided a protocol from an outside source, you must develop one. The following is the "Henry Ford Health System "IRB Protocol Format".

1. PURPOSE: State in one or two sentences the purpose or objective of this project. The goal of this study is to evaluate the effectiveness of different formulations of bupivacaine infiltrated into the transversus abdominis plane (TAP) on post-operative pain management after open abdominal hysterectomy.
2. SPECIFIC AIMS: Number your aims so that the aims can be referred to in the Project Design and Data Analysis sections of this outline. 1) To determine if a TAP block with liposomal bupivacaine provides effective post-operative analgesia after open abdominal hysterectomy. 2) To determine if the mixing of liposomal bupivacaine with bupivacaine hydrochloride provides improved analgesia as compared to either drug alone when used for a TAP block.
3. RATIONALE FOR THE PROJECT:

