 - a. State the rationale for the project and support it with background information about the project. Critically evaluate existing knowledge, and specifically identify the gaps in knowledge the project will fill. Liposomal bupivacaine is a novel formulation of the local anesthetic bupivacaine in which the drug is encapsulated and slowly released over time up until 72 hours post-injection. Since liposomal bupivacaine is slow-released, liposomal bupivacaine may provide delayed post-operative analgesia. Bupivacaine hydrochloride typically provides 24-48 hours of analgesia. We hypothesize that the combination of liposomal bupivacaine to bupivacaine hydrochloride will provide superior analgesia both immediately and up to 72 hours post-operatively. Liposomal bupivacaine was initially FDA approved for surgical site infiltration and has been recently FDA approved for infiltration in the transversus abdominus plane. TAP blocks are routinely used as a part of multimodal analgesia to decrease pain scores and decrease opioid consumption after abdominal surgery. Liposomal bupivacaine infiltrated into the TAP plane has been shown to be effective for post-operative analgesia after robotic prostatectomy, laparoscopic colorectal surgery, and abdominal hernia repair; however, those studies did not compare the effectiveness of liposomal bupivacaine to bupivacaine hydrochloride or to the mixture of Liposomal Bupivacaine and Bupivacaine HCL. Our experience at Henry Ford Hospital suggests that TAP blocks with liposomal bupivacaine provides similar analgesia as those with bupivacaine hydrochloride. This year, a randomized controlled single blinded study comparing liposomal bupivacaine to bupivacaine hydrochloride for TAP blocks for patients undergoing laparoscopic assisted donor nephrectomy showed no difference in pain scores or opioid consumption within the first 48 hours post-operatively. Opioid consumption was slightly decreased 48-72 hours post-operatively in the liposomal bupivacaine group.
 - b. State the applicant's prior research and experience in this research area. As a quality improvement initiative, we have retrospectively reviewed the effectiveness of TAP blocks with liposomal bupivacaine and bupivacaine hydrochloride for post-operative analgesia after laparoscopic assisted colectomy and open abdominal hysterectomy. As members of the regional anesthesia division, we have extensive experience performing TAP blocks for a wide range of abdominal surgical procedures.

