- d. Provide a tentative schedule for conducting and completing this project and, if applicable, the multicenter study. We anticipate one year to recruit patients and collect data. Data analysis will take a few months after study completion.
- e. **Data collection:** Submit a copy of the data collection tool or list the data fields to be collected (review IRB policy, Access to Medical Records for Research). Age, ASA classification, height, weight, BMI, indication for hysterectomy, surgeon, duration of surgery, time of TAP block, time to first break-through analgesic, cumulative analgesic doses and pain scores at rest and with movement in PACU and in the following time periods: 0-24 hours, 25-48 hours, 49-72 hours. in 6 hr increments for the first 24hrs, then every 12 hrs for the next 24 hours. Satisfaction (ie not satisfied, satisfied, very satisfied), length of stay in the hospital, presence of ambulation, presence of nausea and vomiting, evidence of local anesthetic toxicity, presence of hypotension.

7. DATA ANALYSIS: Describe the analysis of the data and relate this to the specific aims in detail. Case reports and medical record reviews also require a description of the planned data analysis (ie. descriptive, observational). The Committee recommends free consultation with the Division of Biostatistics and Research Epidemiology before IRB submission. Many clinical measurements will be recorded post operation. Some are one-time measurements such as total opioid consumption, and some are repeated measurements such as pain scores. Total 8-9 measuring times for those

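### Aim 2 needs the mixture compared with each drug alone, but Section 7 plans only three-group tests, and Section 8b's 80% is power for the three-group ANOVA, not for Aim 2

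*Combined protocol and SAP*

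**What the plan says.** Section 2 (Aim 2) asks whether mixing the two drugs "provides improved analgesia as compared to either drug alone". Section 3a states the matching hypothesis, that the combination "will provide superior analgesia both immediately and up to 72 hours post-operatively". Section 5b says that "the control population is the group receiving 0.25% Bupivacaine". Section 6b lists the outcomes: "Primary outcomes are total opioid consumption, time to the first opioid administration, and pain score during the above mentioned time periods".

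Section 7 assigns one-way ANOVA to total opioid consumption, GEE to pain scores and Cox models to time to first opioid. Each is described as assessing the effect of the three formulas, with significance at p<0.05. The section names no contrast, pairwise test or reference group. The 95% confidence intervals it plans are for averages and proportions, not for differences between groups.

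Section 8b states that 30 patients per group "will have 80% power to detect the effect size of 0.33 by using One- Way ANOVA" for total opioid consumption. For pain scores it gives a second effect size of 0.24, also at 80% power, from a repeated one-way ANOVA with correlation 0.5. Both statements concern the three formulas together.

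**The concern.** Aim 2 consists of two directional comparisons, G3-G1 and G3-G2. A three-group test asks a different question, namely whether any of the three means differs from the others. It can be significant because both liposomal arms beat plain bupivacaine while the mixture adds nothing to liposomal alone. In that case the answer to Aim 2 is no, yet the planned test is positive.

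Two things are at stake. First, because the comparison that answers Aim 2 is not named, it could be chosen after the data are seen, across three primary outcomes and several pain periods. Second, the only power stated for opioid consumption belongs to a test that does not answer Aim 2, so the plan does not show how well 90 patients can answer it.

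**Working it through.** **Inputs from the documents.** 90 patients, 30 per group; effect size 0.33 for opioid consumption; effect size 0.24 and correlation 0.5 for pain (Section 8b); significance level 0.05 and 8-9 measuring times (Section 7). The effect sizes are read as Cohen's f, the SD of the group means divided by the within-group SD, because that reading reproduces the opioid figure.

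**Assumptions.** The documents give no expected means or SDs, so the mean patterns below are assumed and differences are in SD units. Contrasts are two-sided at 0.05 with pooled error, and all 30 patients per group are analysed.

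**1. The plan's own figure.** Noncentrality λ = N·f² = 90 × 0.33² = 9.80. With 2 and 87 degrees of freedom the critical F is 3.10 and power is 79.3%. Exactly 80% needs f = 0.333. The stated 80% is reproduced, as power of the three-group test.

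**2. What f = 0.33 means for the contrasts.**
- Only the mixture differs, by d. The SD of the means is d·√2/3 = 0.471d, so d = 0.33/0.471 = 0.70 SD for both contrasts.
- Evenly spaced means 0, d, 2d with the mixture best. The SD of the means is d·√(2/3) = 0.816d, so d = 0.404. Then G3-G1 = 0.81 SD and G3-G2 = 0.40 SD.
- The mixture equals liposomal alone and both are 0.70 SD better than plain. Then G3-G2 = 0.

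**3. Power per contrast.** Each contrast is a t test on 87 degrees of freedom (critical value 1.988) with noncentrality d·√(30/2) = 3.873d. For d = 0.70 this is 2.71, and power is 76%. For 0.808 it is 3.13 (87%), and for 0.404 it is 1.56 (34%). Power for both contrasts favouring G3 comes from simulation, because they share the G3 mean and the pooled SD.

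| Assumed pattern at f = 0.33 | Three-group test | G3-G1 | G3-G2 | Both favour G3 |
|---|---|---|---|---|
| Only the mixture differs | 79% | 76% | 76% | 64% |
| Evenly spaced, mixture best | 79% | 87% | 34% | 33% |
| Mixture equals liposomal alone | 79% | 76% | 5% (no true difference) | about 2.5% |

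The second column is constant because the power of the F test depends on the means only through f. The test therefore cannot tell the third row from the first.

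**4. Opioid differences detectable with 80% power, 30 analysed per arm.** One contrast: 0.731 SD. Both contrasts, with the single-drug arms equal: 0.816 SD.

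**5. Time to first opioid.** Section 8b gives no figure. The shortcut SE(log HR) = √(2/30) = 0.258 gives hazard ratios of about 0.49 for one contrast and 0.45 for both, but it holds only near a hazard ratio of 1. In a simulated three-arm Cox model with 30 events per arm and equal single-drug arms, the SE at these ratios is about 0.28, and power there is only about 76-77%. Reaching 80% needs about 0.475 for one contrast and 0.435 for both.

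**6. Pain, as a side check.** For the between-group test on the average of m time points, λ = 90 × 0.24² × m/(1 + (m−1) × 0.5). That gives 9.22 for m = 8 and 9.33 for m = 9, with power 76.6% and 77.1%. This too is three-group power.

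**The case against.** **The 80% is not misdescribed.** Section 8b ties it to a one-way ANOVA on three formulas and never calls it power for Aim 2. This stands. A reader might infer that the opioid calculation is wrong or that the trial needs more patients; the documents support neither, since the figure reproduces and no target power for Aim 2 is stated.

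**Pairwise results are partly implied.** Section 7 does not say that only a three-group p-value will be reported. Cox and GEE models with a three-level factor give coefficients against a reference group, and Section 5b supplies the natural one. This stands for G3-G1, so it would be too strong to say that the plan leaves out every pairwise comparison. Coding against plain bupivacaine does not display G3-G2, however, and no follow-up to the ANOVA is stated.

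**The low power figures depend on assumptions.** The mean patterns are not in the documents, and the figures for both contrasts apply only if Aim 2 means better than each drug. In the pattern where only the mixture differs, each single contrast has 76%, close to 80%. This stands too: the 33% is one scenario, not an estimate of the trial's chance of success. The limit of the three-group test in the third row does not depend on which pattern is true.

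**The pain figure.** It would be tempting to call Section 8b's 80% for pain an error because the side check gives 77%. The section states neither the F-test variant nor the number of time points, so that reading is not established.

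**Conclusion.** The point holds. Followed as written, Section 7 does not answer Aim 2. G3-G2 is named for no primary outcome, G3-G1 is only partly implied, and a significant three-group test cannot stand in for them. The opioid power statement is right for the test it names, but it does not describe Aim 2. At the same f, Aim 2 power on opioid consumption is 76% per contrast and 64% for both if only the mixture differs. It is 87%, 34% and 33% (G3-G1, G3-G2, both) with evenly spaced means.

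These values rest on the assumed patterns, 30 analysed per group and two-sided 0.05 per contrast; the joint values also rest on reading Aim 2 as better than each drug. The point is one the sponsor should act on. It does not invalidate the design or the sample size.

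**What to change.** **Section 7.** Name G3-G1 and G3-G2 as the Aim 2 tests for each primary outcome, each with an estimate and 95% confidence interval: pooled-error ANOVA contrasts for total opioid consumption, GEE contrasts for pain and Cox hazard ratios for time to first opioid. State that the mixture will be claimed better than either drug alone on an outcome only if both contrasts favour G3 at two-sided 0.05. Because both must succeed, no alpha split is needed between the two. If the sponsor means that beating one drug is enough, the plan should say so and add a multiplicity rule for the pair.

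**Section 8b.** Keep 90 patients. Say that the 80% is power for the three-group test and not for Aim 2. Add the opioid difference detectable with 80% power: about 0.73 SD for one contrast and about 0.82 SD for both (single-drug arms equal, 30 analysed per arm). If a figure is given for time to first opioid, use hazard ratios of about 0.475 for one contrast and 0.435 for both, assuming every patient has an event; do not enter the shortcut values of 0.49 and 0.45. Recheck the pain figure once the number of assessments and the test are fixed, since Section 6b describes the assessments differently from Sections 6e and 7.

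**Cost.** Wording changes, slightly more analysis and a less favourable power statement. No new patients or data.
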